3.2.2. Evidence of Disease Recurrence

Recurrence will be categorised as local/regional or distant. When recurrence is first documented at any site, complete restaging is required to identify all sites of recurrence per CRF.

3.2.2.1. Local or Regional Recurrence

Local or regional recurrence is defined as recurrence in the area of the tumour bed, hilum or mediastinal lymph nodes.

3.2.2.2. Distant Recurrence

Distant recurrence is defined as spread of disease beyond the area of the tumour bed, hilum or mediastinal lymph nodes.

3.2.3. Overall Survival

OS is defined as the time from the date of randomisation until death due to any cause regardless of whether the patient withdraws from randomised therapy or receives another anti-cancer therapy (i.e. date of death or censoring – date of randomisation + 1). The SURVIVE and DEATH modules of the eCRF will be used. Any patient not known to have died at the time of analysis will be censored based on the last recorded date on which the patient was known to be alive (recorded within the SURVIVE module of the eCRF). The date of contact will not be used. Other eCRF pages will not be considered.

For the futility analysis, survival calls will be made strictly after the date of the Data Cut Off (DCO) for the analysis. For the primary analysis and any subsequent analyses, survival calls will be made two weeks following the date of DCO for the analysis. If patients are confirmed to be alive or if the death date is post the DCO date these patients will be censored at the date of DCO. The status of ongoing, withdrawn (from the study) and “lost to follow-up” patients should be obtained by the site personnel by checking the patient’s notes, hospital records, contacting the patient’s general practitioner and checking publicly-available death registries. In the event that the patient has actively withdrawn consent to the processing of their personal data, death dates may be found by checking publicly available death registries where it is possible to do so under applicable local laws.

If a patient is known to have died where only a partial death date is available, then the date of death will be imputed as the latest of the last date known to be alive +1 from the database and the death date using the available information provided:

- a. For Missing day only – using the 1st of the month
- b. For Missing day and Month – using the 1st of January

If there is evidence of death but the date is entirely missing, it will be treated as missing, i.e. censored at the last known alive date.

OS rate at two years (i.e. 730.5 days), three years (i.e. 1095.75 days) and five years (i.e. 1826.25 days) is defined as the proportion of patients alive at the timepoint, estimated from a KM plot of OS at the time of the primary analysis.

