4.3.4 Survival follow-up (up to final OS analysis)

Assessments for survival should be made every 24 weeks up to 5 years (264 weeks) after randomisation and yearly thereafter following disease recurrence. Survival information may be obtained via telephone contact with the patient, patient's family or by contact with the patient's current physician.

In addition to the survival status, the following assessments are required post recurrence as detailed in the study plan ([Table 2](#)).

- Anti-cancer therapy, radiotherapy and surgery
- Serious Adverse event collection (causally related)
- Subsequent response and progression data (PFS) in accordance with local practice until the first confirmed disease progression on a subsequent treatment (not collected post primary analysis or post 'Final DFS analysis' if required)

Survival data will be collected up to the time of the final OS analysis. Patients should be contacted in the week following date of DCO for IDMC and in the two weeks following date of DCO for primary analysis and subsequent analyses. The status of ongoing, withdrawn (from the study), and "lost to follow-up" patients at the time of each of the efficacy analyses should be obtained by the site personnel by checking the patients notes, hospital records, contacting the patient's general practitioner, and checking publicly available death registries. In the event that the patient has withdrawn consent to the processing of their personal data, the survival status of the patient can be obtained by site personnel from publicly available resources where it is possible to do so under applicable local laws.

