5.1.3 Overall Survival

Overall survival is defined as the time from randomisation to the date of death (from any cause) or to the date the patient was last known to be alive.

Following randomisation and up to final OS analysis, patients will be followed up for survival every 24 weeks for 5 years (264 weeks) and then yearly thereafter, until the study is closed.

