8.4 Outcome measures for analyses

8.4.1 Calculation or derivation of efficacy variables

8.4.1.1 DFS

DFS is defined as the time from the date of randomisation until the date of disease recurrence or death (by any cause in the absence of recurrence).

Patients who are disease-free and alive at the time of analysis will be censored at the date of their last follow-up assessment. The DFS time will always be based on scan/assessment dates and not visit dates. If assessments contributing towards a particular visit are performed on different dates, for example, a biopsy confirming disease recurrence following the scan where recurrence was suspected, the date of recurrence will be the earliest of the dates of the assessment that triggered the recurrence.

DFS rate at 2, 3, 4 and 5 years is defined as the proportion of patients alive and disease free at 2, 3, 4 and 5 years, respectively, estimated from Kaplan Meier plots of the primary endpoint of DFS at the time of the primary analysis.

8.4.1.2 OS

OS is defined as the time from the date of randomisation until date of death due to any cause. Any patient not known to have died at the time of analysis will be censored based on the last recorded date on which the patient was known to be alive.

Note: Survival calls will be made in the week following date of DCO for IDMC and in the two weeks following date of DCO for primary analysis and subsequent analyses and if patients are confirmed to be alive or if the death date is post the DCO date these patients will be censored at the date of DCO. Death dates may be found by checking publicly available death registries.

OS rate at 2, 3, 4, and 5 years is defined as the proportion of patients alive at 2, 3, 4, and 5 years respectively, estimated from a Kaplan Meier plot of OS at the time of the primary analysis and any further timepoints. Long-term OS data captured in the long-term OS follow-up will be analysed as described in Section 8.8.

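### SAP 3.2.3 takes the OS last-known-alive date from the SURVIVE form alone, with no fallback for patients whose status is not confirmed at the data cut-off

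*SAP*

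**What the plan says.** The protocol defines OS in 5.1.3 as running to death "or to the date the patient was last known to be alive". Its derivation in 8.4.1.2 says that a patient not known to have died "will be censored based on the last recorded date on which the patient was known to be alive". Neither section names a form or excludes a source.

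SAP 3.2.3 repeats that rule and fixes the source. "The SURVIVE and DEATH modules of the eCRF will be used"; the alive date is the one "recorded within the SURVIVE module of the eCRF"; and then "The date of contact will not be used. Other eCRF pages will not be considered".

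The same SAP section also provides for survival calls after the DCO. Sites must establish the status of ongoing, withdrawn and lost patients from medical notes, hospital files, the family doctor and public death registers. If patients are confirmed alive, or died after the cut-off, "these patients will be censored at the date of DCO". For patients who withdrew consent to data processing, the SAP names only public death registers.

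On when survival status is collected, Protocol 4.3.4 says "Assessments for survival should be made every 24 weeks up to 5 years (264 weeks) after randomisation and yearly thereafter following disease recurrence". Table 1 of the protocol agrees, placing survival status only in the survival follow-up column. Protocol 5.1.3 reads differently, as survival follow-up from randomisation.

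**The concern.** The form chosen as the only source may be the sparsest one for a patient who has not recurred. On the reading in Protocol 4.3.4 and Table 1, such a patient gets SURVIVE entries mainly from the contacts around each DCO. If that patient is lost before the next contact and the site cannot confirm status, the SURVIVE date may be old or absent. The eCRF may meanwhile hold later scans, laboratory results or doses that show the patient was alive. The SAP excludes those pages and gives no rule for a patient with no SURVIVE date.

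Two things follow. First, alive time already known is dropped while deaths still count, which pushes Kaplan-Meier OS down. Second, the endpoints can disagree within one patient: SAP 3.2.1 censors DFS at the last recurrence assessment, so the scan that sets the DFS censoring date cannot be used for OS. OS is in the alpha-controlled testing sequence and landmark OS rates are reported, so its censoring date should be complete and coherent.

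**Working it through.** **Comparing the texts**

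1. *Source.* Protocol 5.1.3 and 8.4.1.2 name no form. SAP 3.2.3 allows SURVIVE only. The SAP is narrower.
2. *Disclosure.* The only OS item in SAP Section 6 (changes from protocol) is a possible later OS analysis. The source restriction is not there.
3. *Internal consistency.* For a partial death date, SAP 3.2.3 and 3.1.3.1 take the later of the completed date and one day after the last date alive found in the database. That is a wider source than the one used for censoring.
4. *Who is exposed.* Patients confirmed alive are censored at the DCO and lose nothing. Deaths come from SURVIVE and DEATH, so the event count does not depend on this rule. Exposure is limited to patients whose status is not confirmed at the DCO. A death-register search can add a death for a patient who withdrew consent to data processing, but it supplies no alive date.

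**Size**

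No figure in the plan depends on the rule, and the number of unconfirmed patients is not given. The shares and gaps below are therefore assumptions.

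*Lost time.* If 5% of the 682 randomised patients each lost 6 months: 0.05 × 682 × 0.5 = 17 patient-years. For scale, with uniform accrual over 28 months and a DCO at 69 months, mean potential follow-up is 69 − 14 = 55 months. That is 682 × 55/12 ≈ 3,100 patient-years before deaths, so the loss is about 0.5%.

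*Design check.* Power for 195 deaths, HR 0.66 and two-sided 4% is Φ(√195/2 × |ln 0.66| − 2.054) = Φ(2.901 − 2.054) = 80.2%. This matches the approximately 80% in SAP 1.3.

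*Simulation.* 700 patients randomised 1:1, exponential OS, placebo median 96 months, HR 0.66, uniform 28-month accrual (the SAP says non-linear), DCO at 69 months, 400 replicates per row. It gives 194-195 deaths, against 195 in the plan. A share of the patients alive at the DCO is censored early, as though other pages showed them alive up to the DCO. The HR is the ratio of exponential event rates, not the planned stratified log-rank estimate. Compare within rows only.

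| Not updated, placebo / active | Time lost | 5-year OS %, placebo | 5-year OS %, active | HR |
|---|---|---|---|---|
| 2% / 2% | 5.5 months | 64.7 → 64.6 | 75.0 → 75.0 | 0.658 → 0.658 |
| 5% / 5% | 12 months | 64.9 → 64.5 | 75.1 → 74.8 | 0.657 → 0.658 |
| 10% / 10% | 24 months | 64.9 → 63.5 | 75.1 → 74.0 | 0.661 → 0.662 |
| 10% / 10% | all (Day 1) | 64.7 → 62.2 | 75.2 → 73.1 | 0.652 → 0.657 |
| 10% / 5% | 12 months | 64.8 → 64.1 | 75.2 → 74.9 | 0.657 → 0.651 |
| 5% / 10% | 12 months | 64.8 → 64.4 | 75.0 → 74.4 | 0.660 → 0.667 |
| 10% / 5% | all (Day 1) | 64.7 → 62.2 | 75.2 → 74.1 | 0.657 → 0.633 |
| 5% / 10% | all (Day 1) | 64.9 → 63.7 | 75.2 → 73.1 | 0.658 → 0.692 |

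The Day 1 rows are an extreme: no SURVIVE date at all. The SAP does not prescribe Day 1 for OS; it is silent.

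**The case against.** A reader might infer that the SAP ignores all other evidence of survival and contradicts the protocol. The documents support neither reading.

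- *Other evidence does enter.* The post-DCO calls and record checks in SAP 3.2.3 and Protocol 3.11 and 4.3.4 are aimed at ongoing, withdrawn and lost patients. Trial visits and scans should normally appear in the notes that the site must consult, and so can reach SURVIVE that way. This stands, and it confines the problem to patients not updated.
- *It is specification, not contradiction.* The protocol names no source; the SAP picks one. The SAP amendment history for December 2018 mentions, for this section, the eCRF pages to use, so the choice was not hidden. It is still narrower than the protocol and is not in the section that lists departures from it.
- *Not using the contact date is no fault.* The section treats the last date known alive as separate from the date of contact, and calls are made after the DCO.
- *Survival follow-up may start at randomisation.* Protocol 5.1.3 reads that way, which would give disease-free patients more SURVIVE entries. The protocol's sections are not uniform on this, so the point cannot rest on either reading alone.
- *Pooling pages has its own hazards.* Imputed adverse event end dates could create false alive dates. On-treatment visits are also more frequent than later ones, so the latest date depends partly on treatment status. A single dedicated source is defensible. The fix limits the first hazard by using observed dates only, and both by applying only to patients not confirmed at the DCO.

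**Conclusion.** The point holds as a minor defect. For patients not confirmed at the DCO, the rule taken literally can censor OS before dates already in the database and before the same patient's DFS censoring date. There is no fallback when SURVIVE has no date.

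The likely direction is slightly low Kaplan-Meier OS, by about 0 to 1.4 points at five years under the assumed 2-10% shares and 5.5-24 month gaps, and up to about 2.5 points in the Day 1 extreme. With equal shares in the two arms the HR moves by about 0.001, or at most 0.005 in the Day 1 extreme. With 5% against 10% it moves by 0.006-0.007 at 12 months lost, and by about 0.02 to 0.03 only if those patients also have no usable date at all. The number of deaths is unchanged.

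These sizes rest on assumed shares and on the original 195-death design, not on the 94-death stage II-IIIA analysis in SAP Section 7. The 17 patient-years is likewise only an illustration. Nothing in the documents shows that the OS comparison itself is unreliable.

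**What to change.** Keep DCO censoring for patients confirmed alive. For all others, define the OS censoring date as the latest actually recorded date, on or before the DCO, in any eCRF module that shows the patient alive: SURVIVE, visits, scans, laboratory, dosing or adverse events. Exclude imputed dates explicitly, since SAP 3.1.3.1 can set adverse event end dates to month-end or 31 December. List the rule in SAP Section 6. The SURVIVE-only version can stay as a sensitivity analysis.

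The cost is some extra programming and checking of source dates; no new data collection is needed.

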4.3.5 Survival follow-up in the study extension for long-term OS analysis

For patients who consent to long-term OS follow-up, assessments for survival should be made yearly until approximately 10 years after the last patient is randomised.

Survival information may be obtained in-person or via telephone contact with the patient, patient's family, or by contact with the patient's current physician. Please refer to [Table 3](#) for further details.

At the time of analysis, the patient will be contacted for survival status in the 2 weeks following the date of DCO for the long-term OS analysis.

The status of ongoing, withdrawn (from the study), and “lost to follow-up” patients should be obtained by the site personnel by checking the patient’s notes, hospital records, contacting the patient’s general practitioner, and checking publicly available death registries.

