1.3. Number of Patients

Approximately 700 patients will be randomised globally in a 1:1 ratio (AZD9291: placebo) to this study. The primary endpoint of the study is DFS based on investigator assessment. DFS will first be tested in the subset of patients with Stage IIA-III A cancer. If statistical significance is shown for DFS in the subset of patients with Stage IIA-III A cancer, then it will be tested for the overall population with the test mass split between first and second analyses.

The primary analysis of DFS will occur when approximately 247 disease recurrence events have been observed in approximately 490 patients who are in Stage IIA-III A (i.e. non-IB). If the true DFS hazard ratio (HR) for the comparison of AZD9291 versus placebo in this patient population is 0.70, 247 disease recurrence events will provide 80% power to demonstrate a statistically significant difference in DFS at a 5% two-sided significance level (translating to an improvement in median DFS from 40 months to 57 months, assuming DFS is exponentially distributed). The minimum DFS HR that would be statistically significant (i.e. $p < 0.05$, two-sided) is 0.78.

If the true DFS HR for the comparison of AZD9291 versus placebo in the overall population is 0.70, 314 disease recurrence events will provide approximately 90% power to demonstrate a statistically significant difference in DFS at a 4% two-sided significance level (translating to an improvement in median DFS from 46 months to 66 months, assuming DFS is exponentially distributed). The minimum DFS HR that would be statistically significant (i.e. $p < 0.04$, two-sided) is 0.79.

At the time of the primary analysis it is anticipated that approximately 195 OS events (28% maturity) will have occurred (assuming a median OS of 96 months for the placebo arm) in the overall population. If the true OS HR for the comparison of AZD9291 versus placebo is 0.66, 195 death events provide approximately 80% power to demonstrate a statistically significant difference at the 4% (two-sided) significance level. With 195 death events and assuming a true OS HR of 0.85 there is approximately 90% chance of observing an HR < 1.02 .

Assuming 28 months non-linear recruitment the data cut-off for the primary analysis is estimated to occur approximately 68-70 months after first patient randomised.

It is estimated that 3200 patients will be screened in order to randomise 700 patients.

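### Known deaths with no recorded date are censored in the OS analysis; they should count as events when death is shown to fall on or before the data cut-off

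*SAP*

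**What the plan says.** SAP 3.2.3 defines OS as time from randomisation to death from any cause. Its general censoring rule is "Any patient not known to have died at the time of analysis will be censored based on the last recorded date", meaning the latest record that shows the patient living. Protocol 8.4.1.2 has the same rule and says nothing about missing death dates.

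For incomplete dates, SAP 3.2.3 distinguishes two cases, and SAP 3.1.3.1 repeats both:

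- **Partial date.** "If a patient is known to have died where only a partial death date is available, then the date of death will be imputed", taking the later of the last known alive date + 1 and a date built from the known parts. The branches are a missing day, and a missing day and month ("For Missing day and Month – using the 1st of January"). The patient is an event.
- **No date at all.** Where there is "evidence of death but the date is entirely missing, it will be treated as missing, i.e. censored at the last known alive date", the patient is not an event.

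Deaths after the data cut-off are censored at the cut-off. SAP 4.3.7.2 analyses OS by the DFS methods but leaves out the sensitivity analyses. Protocol 4.3.4 and 4.3.5 require sites to establish vital status from notes, hospital records, the patient's doctor and by "checking publicly available death registries".

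**The concern.** A patient with evidence of death is outside the group for which the general rule allows censoring. Kaplan-Meier and log-rank methods assume that censoring is unrelated to the risk of death. Under this rule a patient is censored because of having died.

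Two things are at stake. If undated deaths are equally common in both arms, the HR is little affected but the OS rates read too high. If they are more common in one arm, that arm loses events and the HR shifts. The plan has no OS sensitivity analysis that would show either effect.

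The SAP also treats nearly equal ignorance very differently. Take a patient last known alive in June who is known only to have died in that calendar year. The later of 1 January and last known alive + 1 is the second, so the patient is an event on that day, and nothing from the death date sets the timing. If the year is unknown too, the same known death becomes a non-event.

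**Working it through.** **Inputs.** From SAP 1.3: 195 deaths, HR 0.66, 4% two-sided, about 80% power, placebo median OS 96 months, about 700 patients randomised 1:1, 28 months of accrual, cut-off at 68-70 months. From SAP section 7: final OS analysis at about 94 stage II/IIIA deaths, overall 5% two-sided. The number of undated deaths is in neither document, so every count or share of them below is an assumption.

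**1. The plan's own figure.** The SAP says "195 death events provide approximately 80% power to demonstrate a statistically significant difference at the 4% (two-sided) significance level". With power = Φ(½·√d·|ln HR| − z):

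- ½ × √195 × 0.4155 = 2.901; 2.901 − 2.054 = 0.847; Φ(0.847) = 80.2%.

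The stated power reproduces and is not in dispute.

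**2. Loss of events.** One death in 94 is 1/94 = 1.06%. Removing k undated deaths in the same formula, at HR 0.66:

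| k (assumed) | 195 deaths, 4% | 94 deaths, 5% |
|---|---|---|
| 0 | 80.2% | 52.2% |
| 2 | 79.7% | 51.3% |
| 5 | 79.1% | 50.0% |
| 10 | 78.0% | 47.8% |

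The 94-death column is illustrative, since the documents state no power for 94 deaths. The loss is small for a handful of cases.

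**3. Bias.** This was simulated with 2,000 trials per scenario: 350 patients per arm, exponential survival, the SAP's median and HR, and cut-off at month 69. Three further assumptions were needed: uniform accrual (the SAP says non-linear), last known alive dates on a 24-week grid, and undated deaths chosen at random within arm. The simulated trials averaged about 195 deaths, matching the SAP. Each cell shows all dates known / censored as now / event at last known alive + 1 day.

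| Undated, placebo / active | Mean undated deaths | HR | Placebo 5-year OS (%) |
|---|---|---|---|
| 1% / 1% | 2.0 | 0.666 / 0.666 / 0.666 | 64.83 / 65.11 / 64.84 |
| 3% / 3% | 5.8 | 0.665 / 0.665 / 0.665 | 64.85 / 65.69 / 64.88 |
| 5% / 5% | 9.8 | 0.662 / 0.663 / 0.662 | 64.90 / 66.31 / 64.94 |
| 5% / 0% | 5.7 | 0.661 / 0.694 / 0.660 | 64.86 / 66.26 / 64.91 |
| 0% / 5% | 4.1 | 0.663 / 0.630 / 0.663 | 64.93 / 64.93 / 64.93 |

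Balanced undated deaths leave the HR alone but raise the 5-year rate by 0.3 to 1.4 percentage points. One-sided undated deaths move the HR by about 0.03, towards 1 or away from it depending on the arm. In these runs the imputed version stays within 0.001 of the full-data HR and within 0.05 points of the full-data rate.

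**4. Rough check at 94 deaths.** At HR 0.66, a crude split is 94 × 0.66/1.66 = 37.4 active and 56.6 placebo deaths. Dropping two placebo deaths gives 37.4/54.6 = 0.684. Dropping two active deaths gives 35.4/56.6 = 0.625. This ratio ignores follow-up time and shows scale only.

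**The case against.** The strongest reply is that this is a deliberate, prespecified rule, worded identically in two sections, for a case that should hardly arise. Sites must search several sources, and protocol 8.4.1.2 names registries as a place where death dates may be found. A death learned of at yearly contact can usually be placed in a year, and the partial-date rule then applies. The final OS analysis is triggered by a count of observed deaths, so balanced losses might delay it rather than weaken it; the documents do not say whether undated deaths count. All of this stands, and it keeps the point minor. It does not make censoring a known death correct when a case does occur.

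Four stronger readings might be inferred, and the documents do not support them:

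- **The SAP breaks its own imputation rule.** It does not. That rule is written for partial dates only and has no branch for a missing year. Using its last-known-alive term here is an extension.
- **The patient is carried as alive to the cut-off.** No. The patient leaves the risk set at the last known alive date.
- **The extension's yearly contact puts undated deaths among the 94.** It cannot, because the extension begins after the final OS analysis.
- **The OS result favours osimertinib because of this rule.** No counts by arm are given, so neither presence nor direction of bias can be claimed.

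A simple change to counting every undated death would also be wrong. Survival calls are made after the cut-off, so an undated death learned of then may fall after it.

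**Conclusion.** The point holds as a minor one. The rule censors patients because they died, against the documents' own general condition for OS censoring, and no planned OS analysis would reveal the effect. Each case is about 1% of the 94 planned stage II/IIIA deaths. With 1% to 5% of deaths undated in both arms, 5-year OS reads 0.3 to 1.4 points too high and the HR is unchanged. An HR shift of about 0.03 needs 5% undated in one arm and none in the other, which nothing in the documents suggests. These sizes rest on the assumed shares and on the simulation's accrual and contact pattern. No stated figure in the plan is wrong.

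Protocol 8.8 describes formal testing as complete and plans no p-values for the long-term analysis. What remains open is therefore descriptive: HRs and survival rates, the latter being what balanced undated deaths distort. The SAP of June 2020 predates the extension, so its rule would be expected to carry over unless amended.

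**What to change.** Amend SAP 3.1.3.1 and 3.2.3:

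1. If the death date is wholly missing and death is shown to have occurred on or before the data cut-off, count an event at last known alive date + 1.
2. If death is not shown to precede the cut-off, keep the patient censored as now.
3. Report the number of wholly undated deaths by arm.
4. Add two OS sensitivity analyses: the present censoring rule, and death dated at the day evidence of it was obtained, capped at the cut-off.

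Apply this to the long-term OS analysis. In any re-reporting of the final OS analysis, use it as a sensitivity analysis only, because that analysis has been tested under the existing rule. Section 3.1.3.1 is general, so the amendment should also say whether it governs other endpoints that include death.

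**Cost.** A short SAP amendment and two extra runs, with no new data beyond what sites already seek except recording when evidence of death was obtained. Because it redefines an event after unblinding, it should be dated and justified as such. The downside is that last known alive + 1 is the earliest possible death date, so OS rates may read slightly low, more so with yearly contact. The late-dated sensitivity analysis brackets this. If there are no such deaths, nothing changes.
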